3.8 LONGER-TERM FOLLOW-UP

Upon completion of the trial, participants will be allowed to keep the MAD(s) they prefer. All participants will then be followed up at one and two years (+/- 3 months) after completing the trial. Follow up will either be after a routine clinic appointment or by post. This follow-up is to assess long-term MAD use (or use of alternative treatment) including symptom control, tolerability, adherence, side effects and withdrawal, in addition to HRQoL.

Each follow up will involve the completion of questionnaires (SF-36, SAQLI, ESS and FOSQ) and questions about tolerability, adherence and side effects of MAD as was performed during the main trial. Participants who have continued using a MAD will also be asked if they have had any dental work performed and have their bite measured using a ruler. If attending a clinic appointment weight will also be recorded. The follow-up assessments are summarised in Table 5.

Participants will be informed about the follow-up study at trial completion and initial interest recorded. Approx. 1 month prior to the clinic appointment closest to one year after trial completion, participants will be posted the follow-up participant information sheet along with a covering letter asking if they would consider taking part. Participants will then be called approx. 1 week later to see if they are interested in taking part. If so, the participant will be seen following their routine clinic appointment. Written informed consent will be obtained. If participants are happy to take part in the trial but are unable to stay beyond their clinic appointment then participants will be asked to return the questionnaires in a stamped addressed envelope which will be provided.

Participants who do not have a clinic appointment booked within 3 months of the anniversary of trial completion will be posted the follow-up participant information sheet, consent form, questionnaires and covering letter. They will then be called approx. 1 week later to see if they are interested in taking part. If so, the participant will be asked to complete and return the consent form and questionnaires. Participants who do not initially respond will be contacted once by phone and once by letter to remind them to complete the questionnaires.

All participants who are followed up at year one will be contacted the following year to arrange follow up for year two. The year two follow up will be the same as year one, apart from consent will not be taken again.

If a participant declines follow up at year one this will be recorded and they will not be contacted the following year.

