Adherence to treatment will be assessed using patient sleep diary. Participants will be asked to record the number of hours MAD was used each night and number of nights used each week. Adherence defined as use ≥ 4 hrs per night and ≥ 5 nights per week. If the participant has not completed the patient diary they will be asked to make their best estimate of their hours/nights use.

Stage of trial	Data to be collected					
Screening	Confirmation of eligibility and application of					
	inclusion/exclusion criteria					
Baseline	Basic participant characteristics (age, sex, body mass index					
	(BMI), neck circumference, waist-hip ratio, cardiovascular					
	disease risk factors, blood pressure)					
	Respiratory PSG					
	ESS, FOSQ					
	HRQoL measures – SF-36, EQ-5D and SAQLI					
	Health care usage and driving questionnaire (RTAs)					
Crossover Treatment Periods 1-4	Two week acclimatisation phase					
	Adherence/Retention					
	Tolerability					
	Participant contact with research staff/maxillofacial laboratory					

	Four week treatment phase
	BMI, neck circumference, waist-hip ratio, blood pressure
	Respiratory PSG
	ESS, FOSQ
	HRQoL measures – SF-36, EQ-5D and SAQLI
	Daily sleep diary (including Partner VAS snoring score)
	VAS satisfaction with MAD
	Health care usage and driving questionnaire (RTAs)
	Side effects, withdrawals and adherence.
Treatment Period 4	Participant MAD / no treatment order of preference
Follow up Years 1 - 2	ESS, FOSQ
	HRQoL measures – SF-36 and SAQLI
	Tolerability
	Side effects, withdrawals and adherence
	BMI
	Bite measurement

Table 4. Outcome Measures Collection

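### At years 1 and 2 the dental-work question goes only to participants who have continued using a MAD, so any description of long-term dental work depends on continued use, which dental harm can itself affect

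*Protocol*

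**What the plan says.** Protocol section 3.8 sets up a longer-term follow-up with broad coverage: "All participants will then be followed up at one and two years (+/- 3 months) after completing the trial". Its stated purpose takes in people who have stopped as well as those who have not: "This follow-up is to assess long-term MAD use (or use of alternative treatment) including symptom control, tolerability, adherence, side effects and withdrawal". Participants leave the trial with a device available to them ("Upon completion of the trial, participants will be allowed to keep the MAD(s) they prefer"), and contact is simple: "Follow up will either be after a routine clinic appointment or by post".

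Everyone followed up completes the questionnaires and answers "questions about tolerability, adherence and side effects of MAD as was performed during the main trial". One further element is then added for a subset: "Participants who have continued using a MAD will also be asked if they have had any dental work performed and have their bite measured". The second contact keeps the same content: "The year two follow up will be the same as year one, apart from consent will not be taken again".

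Table 4 (section 3.9) lists for years 1 and 2 the sleepiness and quality-of-life questionnaires, tolerability, "Side effects, withdrawals and adherence", BMI and bite measurement. Table 5 (section 3.10) agrees and adds patient satisfaction. Neither table has a dental-work item.

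**The concern.** Whether a participant still uses a MAD at one or two years is an outcome of treatment. Section 10.1 lists gum and tooth discomfort, loose teeth and malocclusion among the expected reactions. Any of these could plausibly lead to dental treatment, to giving up the device, or to both. A dental-work question put only to continuing users therefore selects respondents on something that the event of interest may have influenced. Those for whom dental treatment was part of the reason for stopping are among those not asked.

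What is at stake is the long-term dental safety description. Section 10.1 calls describing tolerability and adverse events an important aim of the trial, and years 1 and 2 are the only scheduled contacts after months of unsupervised use. An answer that was never requested cannot be recovered at the analysis stage, so an analysis plan cannot repair this.

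**Working it through.** The protocol states no figure for this point, so the check is a reading of who is asked what.

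**Step 1. Who is in scope.** Section 3.8 follows up all participants who consent, and its purpose names withdrawal and use of alternative treatment. Stoppers are in scope.

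**Step 2. Who gets the dental-work question.** The preceding sentence gives every followed-up participant the questionnaires and the tolerability, adherence and side-effect questions. The next sentence adds dental work and bite measurement for continuing users. Year 2 is stated to be the same, so the restriction applies twice.

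**Step 3. Does another named item reach stoppers?**

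| Item | Reaches stoppers at years 1 and 2? | Names dental treatment? |
|---|---|---|
| Tolerability, side effects, adherence (section 3.8, Tables 4 and 5) | Yes | No; dental symptoms may be noted |
| Withdrawals (Tables 4 and 5) | Yes | No; a dental reason for stopping may be noted |
| Bite measurement (section 3.8, Tables 4 and 5) | No, by section 3.8 | No |
| Health care usage questionnaire (Table 5) | Not scheduled at either year | Not applicable |
| Adverse event recording (section 10.1) | No; ends at the last trial visit or at withdrawal from the trial | Not applicable |

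Table 5 marks bite measurement at both years without repeating the restriction, but that does not extend the dental-work question to anyone else. No named item asks followed-up stoppers whether they had dental treatment.

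**Step 4. Contact intervals.** These follow from section 3.8 and show only how long a period could go unasked.

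- Year-1 window: 12 ± 3 = 9 to 15 months after the trial.
- Year-2 window: 24 ± 3 = 21 to 27 months.
- Gap between contacts: at least 21 − 15 = 6 months, at most 27 − 9 = 18 months.
- Scheduled device use in the trial: 3 devices × 6 weeks = 18 weeks.

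Take continued use to mean use at the time of contact. A participant who used a MAD after the trial and stopped just before the year-1 contact would then have 9 to 15 months of post-trial use with no dental-work question. One who answered at year 1 and stopped just before year 2 would have 6 to 18 further months unasked. One who stopped at the end of the trial would be unasked to 21 to 27 months, but had only about 18 scheduled weeks of device use, so later dental work says less about long-term use.

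**Step 5. What cannot be computed.** The protocol gives no stopping rate, no dental-work rate and no follow-up uptake. Follow-up needs separate consent, and those who decline at year 1 are not contacted at year 2. No count of missed events, proportion or bias follows from the text.

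**The case against.** The strongest reply is that the protocol contradicts nothing here. Dental work is not a listed outcome, is not in Table 4 or Table 5, and is not named in the purpose of the follow-up. It shares a sentence and a condition with the bite measurement, and dental work can alter the bite, so the question may be there only to help interpret that measurement. This is a coherent reading, and it is a good reason to leave the bite restriction alone. But the protocol does not state that purpose, and whatever the intent, this is the only dental-treatment question at follow-up, placed under a condition that dental harm can affect.

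A second reply is that stoppers are not ignored. This stands in part. Side-effect and withdrawal items reach them. In the main trial these are asked according to a case report form that is not part of the document. A withdrawal item on such a form could record a dental reason for stopping. A reader might infer that dental reasons for stopping go wholly unrecorded; the protocol does not support that. It supports only that no named item asks stoppers about dental treatment.

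A third reply is that continued use is undefined and might include someone who used a MAD after the trial and stopped before the contact. The wording allows this, but more naturally describes current users. The ambiguity is itself a reason to drop the condition.

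A reader might also infer that the long-term dental-work rate will be understated by a calculable amount. That is not supported. No such rate is planned, and neither size nor direction can be derived. The month figures are contact intervals for hypothetical participants, not a measure of lost events.

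**Conclusion.** The point holds as a minor weakness in a stated data-collection rule. Any description of dental work at years 1 and 2 will be conditioned on continued MAD use, a status that dental harm can influence. Dental symptoms in stoppers, and possibly a dental reason for stopping, may still be captured through other items, but dental treatment is not asked about by any item the protocol names.

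No primary, randomised or planned comparative analysis is touched, and no size or direction of bias can be stated. The conclusion rests on two assumptions: that continuing to use a MAD means use at the time of contact, and that the unseen case report form has no separate dental-treatment question for stoppers. If either fails, the gap narrows or closes in practice, although the text of section 3.8 would still need to say so.

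**What to change.** In section 3.8, separate the two halves of the sentence. Ask every participant followed up at years 1 and 2 whether they have had dental work since the last contact. For those who have stopped using a MAD, add whether it came before stopping or led to it. Keep the bite measurement for current users. Add the dental-work item to Tables 4 and 5 so that the schedule matches the text.

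Describe the answers by current use. Do not treat stoppers as an unexposed control group, because every participant is scheduled to receive each MAD during the trial.

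The cost is one condition removed from an existing question and one short sub-item, for people already being contacted in clinic or by post. No visit, examination or staff time of substance is added. The downside is that some dental work unrelated to the device will be recorded, and attribution to the MAD will remain uncertain.

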3.9 OUTCOME MEASURES

Schedule: Table 4 summarises outcome measures. Apart from patient preference, all outcomes will be assessed at baseline and at the end of each crossover phase (*i.e.* 5 times in total). See Section 3.7 for the schedule of events.

Primary Outcome:

i. Apnoea-Hypopnoea Index (AHI). AHI is the frequency of apnoeas and hypopneas per hour of study [6].

Respiratory PSG: All participants will undergo respiratory PSG monitoring in their own home using Embletta (Medcare) equipment to determine the AHI at baseline and following each treatment period. The Embletta system is fully compliant with British Thoracic Society and the Association for Respiratory Technology & Physiology recommendations [8] for portable monitoring in OSAH. Its diagnostic signals include body position, pulse oximetry, oronasal flow, nasal pressure, snoring and two respiratory effort signals through XactTrace Respiratory Inductive Plethysmograph (RIP) sensors.

All respiratory PSG studies will be scored manually by a NHS Polysomnographer according to the American Academy of Sleep Medicine (AASM) guidelines [6]. Throughout the study, 5% of studies will be scored in parallel by a second Polysomnographer to ensure inter-rater agreement and adherence to recommended guidelines.

Secondary Outcomes:

- i. Epworth Sleepiness Scale (ESS). Subjective daytime sleepiness is a key feature of OSAH resulting from disrupted sleep. This measure has been included as an important secondary outcome as the effective control of sleepiness is a main aim of treatment.
- ii. Physiological indices from the respiratory PSG 4% Oxygen Desaturation Index, mean, minimum and time <90% of nocturnal SpO2
- iii. Blood Pressure*
- iv. Functional status (Functional Outcome of Sleep Questionnaire, FOSQ)* and Generic (SF-36)
- v. Disease specific HRQoL (Calgary Sleep Apnoea Quality of Life Index, SAQLI)*
- vi. EuroQol EQ-5D transformed to the utility scale*
- vii. Adherence, hours use and retention (assessed by a daily sleep diary)
- viii. Snoring scale* (Partner rated visual analogue scale)
- ix. Health care usage and driving and RTA questionnaire (health economic modeling)
- x. Side effects; withdrawals; and participant satisfaction* and preference*

*Outcome measured for research purposes

MAD Adherence

Adherence to treatment will be assessed using patient sleep diary. Participants will be asked to record the number of hours MAD was used each night and number of nights used each week. Adherence defined as use ≥ 4 hrs per night and ≥ 5 nights per week. If the participant has not completed the patient diary they will be asked to make their best estimate of their hours/nights use.

Stage of trial	Data to be collected					
Screening	Confirmation of eligibility and application of					
	inclusion/exclusion criteria					
Baseline	Basic participant characteristics (age, sex, body mass index					
	(BMI), neck circumference, waist-hip ratio, cardiovascular					
	disease risk factors, blood pressure)					
	Respiratory PSG					
	ESS, FOSQ					
	HRQoL measures – SF-36, EQ-5D and SAQLI					
	Health care usage and driving questionnaire (RTAs)					
Crossover Treatment Periods 1-4	Two week acclimatisation phase					
	Adherence/Retention					
	Tolerability					
	Participant contact with research staff/maxillofacial laboratory					

	Four week treatment phase
	BMI, neck circumference, waist-hip ratio, blood pressure
	Respiratory PSG
	ESS, FOSQ
	HRQoL measures – SF-36, EQ-5D and SAQLI
	Daily sleep diary (including Partner VAS snoring score)
	VAS satisfaction with MAD
	Health care usage and driving questionnaire (RTAs)
	Side effects, withdrawals and adherence.
Treatment Period 4	Participant MAD / no treatment order of preference
Follow up Years 1 - 2	ESS, FOSQ
	HRQoL measures – SF-36 and SAQLI
	Tolerability
	Side effects, withdrawals and adherence
	BMI
	Bite measurement

Table 4. Outcome Measures Collection

3.10 VISIT SCHEDULE AND ASSESSMENTS

Visits should be scheduled and performed according to Table 5.

Study Phase	Scree	ening/	8 11	Phase	Phase	Phase	Phase	Follo	w Up
	Base	eline		1	2	3	4		_
Visit No	V1	V2	V3/4	V5/6	V7/8	V9/10	V11/12		
Weeks	W1	W1		W9	W17	W25	W33	Year 1	Year 2
Inclusion/exclusion criteria	×								
Written informed consent	×							×	
Basic demographics	×1								
Medical history	×1								
Clinical examination	x 1	×		×	×	×	×	(weight)	(weight)
Respiratory PSG	×1			x	×	×	×		
Randomisation			×						
MAD measurement			×						
MAD fitting			×						
Blood Pressure		×		x	×	×	×		
ESS	×			x	×	×	×	×	x
FOSQ	×			x	×	×	×	×	x
SF-36	×			x	×	×	×	×	x
SAQLI	×			x	×	×	×	×	x
EQ-5D	×			x	×	×	×		
Partner VAS snoring scale				x	×	×	×		
Health care usage and driving	×			x	×	×	×		
Side effects				x	×	×	×	×	x
Daily sleep diary				x	×	×	×		
Withdrawals				×	×	×	×	×	×
Adherence				×	×	×	×	×	×
Patient satisfaction				×	×	×	×	×	x
Patient preference							×		
Bite measurement								×	x

¹ assessed at screening but also acts as a baseline measure

Table 5. Assessment Schedule

4. ECONOMIC EVALUATION

4.1 Economic Evaluation of the Crossover RCT: McDaid et al [9] concluded that MAD/dental devices may be a treatment option for moderate disease but it remains unclear precisely what type of device may be effective. This was a result of a lack of high quality evidence on their effectiveness. The economic evaluation element of the cross-over trial will provide descriptive data on the resource use, unit costs and health state utilities observed during the 4-week period. The parameter data obtained in the cross-over trial will allow the key uncertainty about the MAD devices to be addressed in a reanalysis of the long term cost-effectiveness model of McDaid et al [9].

Efficacy Parameter Estimates: Health state utilities will be elicited from participants in the cross-over trial using the EQ-5D with the UK social tariff [10]. Systolic blood pressure results will also be collected.

Resource Use and Unit Costs: Resource use and unit costs are being primarily collected to be incorporated into the long term cost-utility. However, mean costs by intervention will be reported for the four week cross-over trial. The perspective for collecting the costs of resource use will be that of the NHS and Personal Social Services (PSS), as advocated in the NICE reference case [11]. Trial protocol driven costs which do not affect participant care outcomes such as administering research questionnaires will be omitted and only health service cost will be included.

Resource use: Resource use data will be collected for the duration of the trial. The type of MAD unit (SP1, SP2 or bMAD) will be recorded as will the frequency of clinic contact (face–to-face clinical contact and telephone consultation) and primary care visits relating to OSAH.

Unit costs: MAD unit costs will be obtained from the finance department of Papworth Hospital. Unit costs for clinician time including labour, capital and overheads will be taken from national estimates [12]. Any medication costs will be taken from the NHS electronics drug tariff [13] or the British National Formulary [14]. The unit costs of any hospital procedures will be taken from the NHS reference costs [15]. In the absence of national estimates, unit costs will be taken from published sources and centre specific costs for Papworth Hospital. Unit costs will be applied to the resource use identified for each participant to obtain mean costs for the entire period of the trial. Costs will be reported in 2007/2008 pounds.

Within-Trial Economic Analysis: Health state utility data will be converted to quality adjusted life years (QALYs) for the four week time horizon of the trial using the area under the curve method. To avoid bias and increase precision in estimates regression adjustment will be applied to costs [16, 17]. Independent variables in the regression adjustment will include MAD group and the potential confounding variable of participants' weight. In addition to regression adjusted results, raw scores will be reported for completeness. Results will be expressed as means accompanied by their 95% confidence intervals. In the event that descriptive statistics suggest skewness of the cost data distribution bootstrap replications will be performed to establish the robustness of results.

- **4.2 Long-term Economic Model:** The aim of the long term economic model is to determine the cost effectiveness of MAD devices for the treatment of OSAH. The objectives are to:
 - 1) Determine the cost effectiveness of MADs compared to a no-treatment control
 - 2) Determine the cost effectiveness of MADs compared to all relevant NHS comparators (no treatment, CPAP, conservative care)

Methods: A cost-utility analysis will be conducted to establish the cost-effectiveness of alternative treatments for OSAH. This will be done by populating a probabilistic Markov cohort process model with the best available data on efficacy, QALYs, resource use and costs.

Economic Model: A new decision analytic model will not need to be developed for this project as McDaid et al [9] developed a model to economically evaluate CPAP for their recently published HTA monograph. The economists that developed the peer reviewed 'York economic model' have agreed to collaborate with the project team, granting us access to the economic model and literature review strategies.

The model characterises the participants' lifetime prognosis using the health states; OSAH, OSAH following coronary heart disease, OSAH following a stroke and death. As OSAH interventions are designed to affect sleepiness and can subsequently affect the risk of road traffic accidents (RTAs), RTAs are also included in the model.

The health effects of OSAH interventions will be expressed in QALYs. The cost of the resource use associated with each intervention will be estimated in accordance with the NICE reference case [11]. An NHS and PSS perspective will be adopted and costs and benefits will be discounted at 3.5%. Costs will be presented in 2007/2008 pounds. Resources that will be costed include the cost of OSAH devices, outpatient appointments, sleep studies, cardiovascular events and RTAs. All cost will include labour, capital and overhead costs, and will be annualised in the case of capital costs.

Transition Probabilities and Resource-Use Data: For MAD arms and the no-treatment arm health state utilities (from EQ-5D), systolic blood pressure (used in conjunction with hypothetical participant characteristics [9]) to predict cardiovascular events using the Framingham risk equations), resource use and unit cost data will be taken from the results of the cross-over trial. All remaining parameter estimates will be obtained by updating the systematic literature review conducted by McDaid et al [9]. The search strategy employed in 2006 will be re-run to identify any relevant data that has emerged in the intervening period. New data will be utilised with previously identified data using conventional meta-analysis techniques based on random effects models.

Analysis: Cost-effectiveness will be summarised as the mean incremental cost per QALY (mean incremental net monetary benefit). Uncertainty surrounding the most cost-effective intervention will be summarised using cost-effectiveness acceptability curves. Parameter uncertainty will be propagated through the model using probabilistic methods/sensitivity analysis. A single stage approach to estimation will be adopted to simultaneously estimate model parameters and cost-effectiveness outcomes of interest, such as mean incremental benefit, CEACs etc. In common with McDaid et al [9] Excel software will be used to synthesize different sources of evidence and implement the model i.e. estimation will be based on Markov Chain Monte Carlo simulation techniques. Uncertainty in fixed parameters and scenarios will be assessed using one-way and multi-way sensitivity analysis.

5. Data Collection

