- a) 2 week Acclimatisation Phase with Telephone Follow-up: The CRA will telephone participants at a prearranged time two weeks after treatment starts with each device to assess initial tolerability, adherence and to record any contact with the RF, maxillofacial laboratory or other clinical staff in the previous two weeks. A standardised written algorithm will be used to provide simple troubleshooting and non-specific behavioural prompts should a participant report non-tolerance/adherence. Clinical issues will be referred to the RF or a study Physician as required.
- b) 4 week Treatment Period: All participants will receive 4 weeks treatment with each MAD and the notreatment control, with outcome assessment at the end of each treatment period.

VISITS 5 and 6 (visit 6 is to return home sleep study equipment)

Participants will return at the end of each treatment phase for outcome assessment. This will involve a clinical examination, including weight, neck circumference, waist-hip ratio, and blood pressure and completion of the questionnaires as per Visit 1 (SF-36, SAQLI, EQ-5D, ESS and FOSQ). In addition they will be asked about any side effects, adherence, satisfaction with the MAD and withdrawals according to the CRF. Participants will return the daily sleep diary.

The CRA or RF will set up the sleep study equipment and they will be asked to return it the following day, along with the current device if on active treatment. A courier service can be arranged for participants who are unable to return the equipment themselves.

Data collection following the no treatment control period will be identical to the three active treatment arms.

1 week wash out period: A one-week washout period (no treatment) following each active treatment will ensure that the effects of the previous device have worn off. The next device will be given to the participant at the visit. Participants will wear the next MAD (or no treatment) according to the intervention schedule before returning for outcome assessment at the end of the treatment period.

VISITS 7, 9,11 and 12 (visits 8 and 10 are to return home sleep study equipment)

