10.1 Adverse Event Reporting

MAD treatment for mild to moderate OSAH has been used extensively in clinical trials and in patient populations. Thus its adverse event profile is generally well known. Description of the tolerability and adverse event profile is an important aim of this trial. It is unlikely that novel (unexpected) adverse events will occur and the adverse event profile is anticipated to be modest.

An adverse event (AE) is defined as 'any untoward occurrence in a participant or clinical investigation subject receiving a trial intervention and which does not necessarily have a causal relationship with this intervention'. An AE can therefore be any unfavourable or unintended sign (including an abnormal laboratory finding), symptom or disease temporally associated with the use of the study intervention, whether or not considered related to the intervention.

Adverse Reactions (AR)

An **AR** is an AE where a causal relationship with the intervention is at least a reasonable possibility i.e., the relationship cannot be ruled out.

Expected Adverse Reactions

MAD therapy is generally very well tolerated. The main expected ARs of MAD therapy are:

Temporomandibular joint / Jaw Discomfort Mouth Discomfort Dry Mouth Excessive Salivation Gum Discomfort Tooth Discomfort Loose Teeth Malocclusion

These ARs can be minimised by careful MAD fitting. The frequency of these ARs will be recorded on the case report forms (CRFs).

Unexpected Adverse Reactions

Mouth ulcers

An Unexpected AR is one which is of a nature or severity that is not consistent with the expected AR profile of the trial intervention. Unexpected ARs will be recorded on the CRFs. The probability of Unexpected ARs is low.

Recording of Adverse Events

For this trial, the AE reporting period is from randomisation to the patient's last trial visit (after the 4th treatment), or until the point of patient withdrawal from the trial. AE recording will be limited to any ARs, any other AE considered by the Principal Investigator to be of medical interest/importance to the trial and all Serious AEs (SAEs – see Section 10.2). AEs will be recorded on the routine CRFs.

It will be left to the investigator's clinical judgement whether or not an AE is of sufficient severity to require the patient's removal from the trial treatment. A patient may also voluntarily withdraw from treatment if they find an AE to be intolerable.

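### The resource-use rule limits primary care visits to those related to OSAH and names no dental care, so the cost of treating device reactions may be missed

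*Protocol*

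**What the plan says.** Section 4.1 sets the perspective: "The perspective for collecting the costs of resource use will be that of the NHS and Personal Social Services (PSS"). Its resource-use paragraph then says what will be recorded over the trial: which device was used, how often there was clinic contact in person or by phone, and primary care visits, the last qualified in the phrase "telephone consultation) and primary care visits relating to OSAH". Dental visits are not mentioned.

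Section 4.2 gives the cost items for the long-term model: "Resources that will be costed include the cost of OSAH devices, outpatient appointments, sleep studies, cardiovascular events and RTAs". It takes resource use for the MAD and no-treatment arms from the crossover trial. The updated literature review supplies the remaining parameters.

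Section 10.1 introduces its list with "The main expected ARs of MAD therapy are" and names "Temporomandibular joint / Jaw Discomfort Mouth Discomfort Dry Mouth Excessive Salivation Gum Discomfort Tooth Discomfort Loose Teeth Malocclusion". It adds that careful fitting can keep these reactions down.

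Three other places touch on this care:
- Section 3.9 lists a "Health care usage and driving and RTA questionnaire (health economic modeling"). Tables 4 and 5 schedule it at baseline and after each of the four periods. Its items are not printed in Appendix 4.
- Section 3.4 has a call two weeks into each device period, to "record any contact with the RF, maxillofacial laboratory or other clinical staff in the previous two weeks". Support-line calls are also counted.
- Section 3.8 provides that participants still using a MAD at years 1 and 2 are "asked if they have had any dental work performed".

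**The concern.** The reactions that the protocol expects are ones a participant would naturally take to a GP or a dentist. NHS care of that kind lies within the stated perspective, but on its plain wording the rule counts a GP visit only if it concerns OSAH, and it counts no dental visit. A visit for jaw pain or a loose tooth caused by the device is a cost of the treatment, not of the disease.

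A gap of this kind would run in one direction against no treatment, because the no-treatment period cannot itself cause a device reaction. It could also differ between devices. The bespoke device is professionally fitted, while the other two are moulded and advanced by the participant, and the protocol itself ties reactions to the care taken in fitting. Whether cost and outcome vary with device sophistication is one of the trial's two main questions. Because the long-term model draws its MAD and no-treatment resource use from the trial, anything not collected there would carry forward. Visits that were never asked about may be hard to recover reliably later.

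**Working it through.** The protocol states no figure on this point, so there is none to reproduce. The check is whether any text brings a GP or dental visit for a device reaction into the costing.

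1. **Section 4.1, resource use.** Primary care is included with the OSAH qualifier. Dental care is not named. A device-reaction visit to a GP is in only if the qualifier is read to cover OSAH treatment.
2. **Section 4.1, unit costs.** Sources are given for clinician time, medication and hospital procedures. Drugs and procedures for a reaction could be priced, but pricing does not bring a GP or dental consultation into the count of resource use.
3. **Section 3.4, week-2 call.** Contact with other clinical staff is recorded without an OSAH restriction, but the look-back is two weeks. A device period lasts 6 weeks, so 6 − 2 = 4 weeks of each period are outside this record.
4. **Section 3.4, support lines.** Calls to the trial team and to the maxillofacial laboratory are counted. These are contacts with the trial's own services, not with a GP or community dentist.
5. **Section 3.9 and Tables 4 and 5, health care usage questionnaire.** It is scheduled 1 + 4 = 5 times, which is the right timing. Whether it asks about GP visits for reactions or about dental visits cannot be seen. The scope in section 4.1 is the only one stated, and a questionnaire built to it would carry the same restriction.
6. **Section 10.1 and the side-effect records.** The frequency of reactions is recorded, but not the care sought for them.
7. **Section 4.2, cost list.** No item covers dental care or treatment of reactions.
8. **Section 3.8, years 1 and 2.** Dental work is asked about, but Table 5 has no health care usage questionnaire at those times and nothing links the answer to costing.

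Steps 2 to 4 capture part of the care. No step clearly captures a GP or dental visit for a reaction.

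**Size.** The omitted cost per participant per device period is p × c, where p is the share making one such visit and c is the cost of a visit. The protocol gives neither. Purely assumed values show how loosely this is determined: p = 0.02 and c = £20 give 0.02 × 20 = £0.40, while p = 0.20 and c = £80 give 0.20 × 80 = £16. That is a 40-fold spread (16 / 0.40) produced wholly by the assumptions, so it is not an estimate.

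**The case against.** The strongest reply is that the instrument which would settle the matter is not visible. The health care usage questionnaire exists for the economic modelling, is given after every period, and may already ask about GP and dental visits. The OSAH qualifier can also bear a wider meaning: the MAD is the treatment for OSAH, so a visit about the device can be called a visit relating to OSAH. The cost list in section 4.2 is introduced as what the costed resources include, so it need not be exhaustive, and item-level definitions are often left to the case report form or an analysis plan. All of this stands, and it removes certainty that the care is left out. It does not remove the point, because the only scope the protocol states is the narrow one and no text widens it.

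The cost may also be small. Section 10.1 describes MADs as well tolerated, and section 3.3 excludes people with significant dental or jaw disease. That stands too, and it is a reason not to attach a sum.

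Three stronger readings are tempting and are not supported:
- A reader might infer a bias against CPAP. Appendix 1 reports mostly similar side effects for MAD and CPAP, and section 4.2 has no cost line for CPAP reactions either, so the net direction is unknown.
- A reader might take the dental-work question at years 1 and 2 as showing that device-related dental work is expected. The question sits beside bite measurement and attributes nothing to the device.
- A reader might carry an assumed six-week cost forward over a lifetime. The protocol offers no basis for a rate that persists.

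**Conclusion.** The point holds as a risk created by the wording. Sections 4.1 and 4.2 do not name GP or dental care for device reactions, although section 10.1 expects reactions of that kind and the NHS perspective would include their treatment. If the text is followed literally, MAD cost is at risk of being understated against no treatment. The comparison between devices is also at risk, provided that reaction rates differ between them. A reader might infer that MAD costs are in fact understated; that cannot be concluded without seeing the questionnaire. No amount, and no effect on cost per QALY or on the ranking of devices, can be derived from the protocol. The conclusion rests on the plain reading of the OSAH qualifier and on the questionnaire following the stated scope. The matter merits correction because it is cheap to settle in advance.

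**What to change.** - In section 4.1, reword the rule to cover *primary care and NHS dental visits relating to OSAH or to the MAD, including treatment of adverse reactions*.
- Confirm that the health care usage questionnaire asks about these visits in all four periods, no treatment included, so that the arms are measured alike. Add one item if it does not.
- In section 4.2, add treatment of device reactions to the list of costed resources, and state that the year 1 and year 2 answers on dental work (section 3.8) are available to inform it.

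The cost is two sentences of protocol text and at most one questionnaire item, with a small added burden on participants. Unit costs can follow the hierarchy of sources already in section 4.1. MAD costs may come out slightly higher, which is the intended consequence of counting this care.
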